5. EFFICACY

The primary analysis set will be the ITT analysis set (see definition in Section 2.3), unless specified otherwise. Efficacy assessments over time will be performed at the analysis time points defined in Section 2.1.3. However, the use of the mITT analysis set (instead of ITT) in the efficacy analyses will be determined based on the impact of the COVID-19 or similar pandemics and assessed prior to the database lock for the first IA during DB study intervention phase.

All efficacy data will be summarized by study Parts 1 and 2, as well as for the whole study data overall:

- For DB study intervention phase: by study intervention arm over time (when applicable), as well as by study part (1 and 2).
- For OL study intervention and Follow-up phases: by study intervention arm over time and by study part 1 and 2. Additional selected efficacy analyses will be conducted to compare the OL study intervention data from Week 52 to Week 148 in Arm 2 with data from the first 96 weeks of DB study intervention in Arm 1 (i.e same duration of exposure to JNJ-3989+NA in both arms). See Section 5.5.1.4 for more details.

Subgroup analyses will be conducted on Part 2 data alone as well as combined data (Part 1 and Part 2) to leverage the total sample size of the entire study. Subgroup analyses will be performed if their size is at least 10% of the total sample size. All analyses will be presented only in a descriptive fashion.

For OL intervention and FU study phases, all efficacy data will be presented only descriptively, and no formal testing will be performed.

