Overall rationale for the Amendments: Based on the observation that in Part 2 of the REEF-D study significant ALT elevations were more frequently observed in participants with HBsAg levels >10,000 IU/mL at screening or at baseline (irrespective of HDV RNA levels), a temporary halt of new enrollment into the study was implemented in December 2022. Since there was no immediate risk to the safety of participants already enrolled in the trial, treatment and monitoring of ongoing participants was continued as per current protocol.

This amendment aligns the Statistical Analysis Plan (SAP) with Protocol Amendment #4 issued on April 7, 2023 which was submitted in context of the Sponsor's strategic decision to discontinue further investment in its hepatitis B and D discovery and development programs. In light of this decision, which was not driven by safety concerns with JNJ-73763989 (JNJ-3989), enrollment of new participants into the REEF-D study will not be reopened.

The overall reason for this amendment is to continue the study in a modified way for participants already enrolled and to describe the reduced sample size in the study. The hypothesis test is no longer going to be performed and the analyses in the study will be descriptive. Per IDMC recommendation, it was added that in Part 2, participants with HBsAg values >10,000 IU/mL at screening or baseline, who were assigned to Arm 1 (placebo), will not roll-over to the open-label phase and will enter the follow-up phase. In addition, the stopping criteria for nucleos(t)ide analog (NA) treatment at Week 144/148 have been updated upon HA request.

Main Changes		
Section Number and Name	Description of Change	Rationale
Throughout the SAP	Sample size for Part 2 was reduced from 145 to 30 patients	The enrollment in the study was stopped so the final Part 2 sample size is 30.
Throughout the SAP	Interim Analysis for Sample Size Re-Estimation has been removed from the SAP.	Due to stopped enrollment, the sample size re-estimation is no longer relevant.
Throughout the SAP	Removed sections on Type I error rate.	The study is now a descriptive study so no Type I error control is required.
Throughout the SAP	Removed wording on multiplicity adjustment	Due to stopped enrollment, the study will only have descriptive analyses
5.5.1.1.12 ALT/AST Elevations 5.5.1.1.11 HBV Flares	Updated Flare definitions	Clarification

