1.5. Randomization and Blinding

Randomization and Stratification

Randomization will be performed using a 4:1 ratio (Active regimen from the start Arm1 : Placebo/deferred treatment Arm 2), regardless of the study part, to minimize bias in the assignment of participants to intervention arms, to increase the likelihood that known and unknown participant attributes (eg, demographic and baseline characteristics) are evenly balanced across treatment arms, and to enhance the validity of statistical comparisons across intervention arms.

Randomization will be stratified by presence of compensated cirrhosis at screening (yes or no) (Part 1 only), HDV RNA testing laboratory location (China versus outside China), and HBeAg status at baseline (positive versus negative) in order to provide an evenly balanced representation across the 2 arms.

Blinding

Blinded treatment will be used to reduce potential bias during data collection and evaluation of clinical endpoints.

The investigators, participants and all site personnel will remain blinded to study intervention allocation until Week 52 (Part 1) and Week 48 (Part 2). After Week 52 (Part 1) and Week 48 (Part 2), it will be communicated to the investigators whether the participants were allocated to either the investigational arm (Arm 1) or the control arm (Arm 2) to allow the correct open-label and follow-up visits schedule to be followed (see Schedules of Activities). For each participant, all HDV RNA, HBsAg, HBeAg, HBcrAg, anti-HBs, and anti-HBe antibody testing individual results will be provided to the investigator and the sponsor for managing the participant's safety.

After Week 52 and up and until Week 144, study intervention will be administered in open-label fashion to all participants (except Part 2 participants allocated to Placebo+NA who had HBsAg >10,000 IU/mL at screening or baseline).

Prior to Part 1 IA1 (see Section 3.3.2.1.1), the Sponsor Committee will review unblinded aggregated interim data of HDV RNA, HBsAg, ALT, AST, total and direct bilirubin, HBV DNA and individual patient profiles for the values/changes from baseline over time for all participants in Part 1 including those randomized to the placebo+NA arm.

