2.1. Analysis Phases and Visit Windows

2.1.1. Analysis Phase

The analysis phases are defined in [Table 1](#) below.

Table 1: Analysis Phases Start and End Dates

Analysis phase	Start date	End date
Screening	The date of signing the informed consent	1 day before the first study agent intake
Double-Blind (DB) Study Intervention	Date of first study agent intake	
If participant did not withdraw from the study and did not discontinue treatment early prior to the projected/actual Week 52 Visit date:
 
Min(Date of Week 52 study agent intake – 1 day, cut-off date*)
 
Otherwise:
 
[Min (Early study withdrawal visit date, study agent discontinuation date) + 5 days^a] or cut-off date*, whichever occurs first

Open-Label (OL) Study Intervention	
If participant has a projected/actual Week 52 Visit date:
 
 – End date of DB study intervention phase + 1 day 
Otherwise:
 
 – Missing 	
If participant did not withdraw from the study prior to the projected/actual Week 144 (Arm 1)/Week 148 (Arm 2) Visit date and did not discontinue treatment early prior to the projected/actual Week 140 (Arm 1)/Week 144 (Arm 2) Visit date:
 
[Min (Date of Week 144 Visit (for Arm 1) or / Date of Week 148 Visit (for Arm 2))+ 5 days^a] or cut-off date*, whichever occurs first
 
if participant withdrew from the study or discontinued treatment between projected/actual Week 52 Visit date + 1 day and projected/actual Week 144 (Arm 1)/Week 148 (Arm 2) Visit date:
 
[Min (Early study withdrawal visit date, study agent discontinuation date)+ 5 days^a] or cut-off date*, whichever occurs first

Follow-up	
If participant did not withdraw informed consent during DB or OL study intervention phases
 
Max (End date of DB study intervention phase, End date of OL study intervention phase) + 1 day
 
Otherwise:
 
Missing
	
If participant entered the Follow-up phase:
 
Max [early study withdrawal visit date, study completion date] or cut-off date, whichever occurs first.
 
Otherwise:
 
Missing

*Cut-off dates will be defined to match the prespecified timepoints for IDMC safety monitoring, interim analysis, the primary analysis and the final analysis, respectively.

^a: Addition of 5 days is only applicable for Adverse Events and Concomitant Medications

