5.5.1.4. Additional Efficacy Endpoints Relative to The Actual Duration of JNJ-3989 Treatment

This section intends to evaluate some selected efficacy endpoints over time conditional upon the same treatment duration with JNJ-3989 across the 2 arms based on Part 2 data. For example, DB

Week 24 for Arm 1 corresponds to Week 76 for Arm 2 (Week 52+24, See [Table 2](#)), as participants in Arm 2 start treatment with JNJ-3989 at Week 52 when they switch over to the active regimen. For each DB Week X for Arm 1 data, the corresponding Week 52+X for Arm 2 data will be considered, as described in [Table 5](#):

Table 5: Correspondence between timepoints for Arm 1 and Open Label timepoints for Arm 2

Analysis Time point for Arm 1 (label)	Matching Analysis OL Timepoint for Arm 2 (label)
Baseline	Week 52
Week 2	Week 54
Week 4	Week 56
Week 8	Week 60
Week 12	Week 64
Week 16	Week 68
Week 20	Week 72
Week 24	Week 76
Week 28	Week 80
Week 32	Week 84
Week 36	Week 88
Week 40	Week 92
Week 44	Week 96
Week 48	Week 100
Week 52	Week 104
Week 56	Week 108
Week 60	Week 112
Week 64	Week 116
Week 68	Week 120
Week 72	Week 124
Week 76	Week 128
Week 80	Week 132
Week 84	Week 136
Week 88	Week 140
Week 92	Week 144
Week 96	EOT (only for OL completers)

When applicable, the reference timepoint (RT) for those analyses will be baseline (DB Day 1) for Arm 1 and Week 52 for Arm 2.

The following endpoints will be presented for those time points during the open-label phase in Arm 2 that match the treatment duration in Arm 1 during the double-blind phase, because of the deferred active trial design, as per [Table 5](#).

The selected endpoints are:

- Proportion of participants with HDV RNA $\geq 2 \log_{10}$ IU/mL decline from RT or HDV RNA TND in combination with normal ALT
- Proportion of participants with HDV RNA $\geq 2 \log_{10}$ IU/mL decline from RT or HDV RNA $<$ LLOQ in combination with normal ALT

- Proportion of participants with HDV RNA $\geq 2 \log_{10}$ IU/mL decline from RT or HDV RNA TND
- Proportion of participants with HDV RNA TND
- Proportion of participants with HDV RNA <LLOQ
- Proportion of participants with normal ALT
- Proportion of participants with LSM reduction ≥ 2 kPa from RT
- Proportion of participants with HBsAg seroclearance i.e. with HBsAg < LLOQ, with HBsAg < 1 IU/mL and < 10 IU/mL
- Change from RT in HDV RNA
- Change from RT in ALT
- Change from RT in HBsAg
- Change from RT in LSM

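### The exposure-matched display sets a low-HBsAg Arm 2 open-label group against an unrestricted Arm 1, and Table 1 has no clean path for placebo participants who do not roll over

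*SAP*

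**What the plan says.** SAP section 5 announces selected analyses that "compare the OL study intervention data from Week 52 to Week 148 in Arm 2 with data from the first 96 weeks" of Arm 1, on the ground that JNJ-3989 exposure is then equal. Section 5.5.1.4 sets this up "conditional upon the same treatment duration with JNJ-3989 across the 2 arms based on Part 2 data" and states, with no exception, that "participants in Arm 2 start treatment with JNJ-3989 at Week 52 when they switch over to the active regimen". Table 5 pairs each Arm 1 week with the Arm 2 week 52 weeks later.

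Section 1.5 gives open-label treatment to all participants "except Part 2 participants allocated to Placebo+NA who had HBsAg >10,000 IU/mL at screening or baseline". The Amendment 5 rationale adds that these participants "will not roll-over to the open-label phase and will enter the follow-up phase". The exception covers the placebo arm only. The same rationale explains that "significant ALT elevations were more frequently observed in participants with HBsAg levels >10,000 IU/mL at screening or at baseline", and that after the December 2022 enrolment halt "treatment and monitoring of ongoing participants was continued as per current protocol".

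Table 1 (section 2.1.1) fixes phase dates. For a participant who neither withdrew nor stopped treatment before Week 52, the double-blind phase ends the day before the Week 52 study-agent intake, or at the cut-off if earlier. The open-label phase starts under the condition "If participant has a projected/actual Week 52 Visit date". Its two end rules cover completing open-label treatment, and withdrawing or stopping treatment after Week 52.

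**The concern.** The matched display is meant to show two groups with the same JNJ-3989 exposure that differ only in when they started. After the roll-over restriction they also differ in HBsAg, because the restriction acts on one arm. By the sponsor's own account the restricting factor goes with ALT elevations. Three of the matched endpoints require normal ALT and a fourth is change in ALT. Several others are absolute HBsAg thresholds, which are harder to reach from a high start: going from above 10,000 to below 10 IU/mL takes a fall of more than log10(10,000/10) = 3 log10. A difference between the columns could therefore be read as an effect of deferring treatment when it reflects who was allowed to switch.

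The second problem is mechanical. Phase dates drive adverse-event allocation (section 6.1.2), by-phase safety summaries (section 6), open-label exposure (section 4.6) and visit windows (Table 2). If they are undefined for completers of placebo who go straight to follow-up, untreated time can be reported under the wrong phase.

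**Working it through.** **Schedule, reproduced first.** Arm 2 open-label exposure is 148 − 52 = 96 weeks, as section 5 says. Four-weekly dosing gives 48/4 + 1 = 13 double-blind injections, the last at Week 48, and (144 − 52)/4 + 1 = 24 open-label injections in Arm 2. Both agree with the compliance denominators in section 4.7. The duration matching is arithmetically sound; the population matching is not.

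**Expected arm sizes.** Part 2 has 30 participants (section 1.4) randomized 4:1 (section 1.2): 30 × 4/5 = 24 in Arm 1 and 30 × 1/5 = 6 in Arm 2. Actual allocation is not stated. One participant in 6 is 16.7 percentage points.

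**Selection offset.** Let f be the share with HBsAg above 10,000 IU/mL, and p_low and p_high the response rates on JNJ-3989 in the two HBsAg strata, with the same drug effect in both arms.

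- Arm 1, unrestricted: (1 − f) × p_low + f × p_high
- Arm 2, open label: p_low, because other secondary endpoints use observed cases (section 5.5) and non-rollovers have no treated data
- Arm 2 minus Arm 1: f × (p_low − p_high)

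Neither f nor the response gap is in the SAP. The table is an illustration over assumed ranges, not an estimate.

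| Assumed f | Expected Arm 2 rolling over, 6(1 − f) | Chance at least one of 6 is excluded, 1 − (1 − f)^6 | Arm 1 above the cut-off, 24f | Offset (points) for an assumed gap of 10 / 20 / 40 points |
|---|---|---|---|---|
| 10% | 5.4 | 47% | 2.4 | 1 / 2 / 4 |
| 30% | 4.2 | 88% | 7.2 | 3 / 6 / 12 |
| 50% | 3.0 | 98% | 12.0 | 5 / 10 / 20 |

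**Table 1 traced for a non-rollover** (last placebo at Week 48, day 337; no Week 52 dose; follow-up entered):

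- *First double-blind end rule.* It needs a Week 52 intake that does not exist, so the end is undefined. If the minimum ignores missing values, the end becomes the cut-off. With an illustrative cut-off at day 800, double-blind ends on day 800 and all follow-up before it is absorbed into the double-blind phase.
- *Second double-blind end rule*, treating the end of placebo as discontinuation on day 337 or 365. The double-blind end is usable (day 337 or 365, plus 5 days for adverse events and concomitant medications only).
- *Open-label start.* It depends on a projected or actual Week 52 visit, not on a dose. If that condition is met, the second route gives an open-label start on day 338 or 366.
- *Open-label end.* The first rule presupposes treatment continuing to about Week 144 and a Week 148 visit. The second covers events from the day after Week 52. A last study-agent date of day 337 or 365 satisfies neither.
- *Follow-up start.* The later of the two end dates plus one day gives day 338 or 366, the same day as the open-label start.

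On that second route, whether an untreated visit is windowed as Week 54 or Week 56, and so paired with Arm 1 Week 2 or Week 4 in Table 5, depends on a choice the SAP does not make.

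**The case against.** The strongest reply is that little rests on this display. It is an other-secondary analysis, section 5 makes all open-label and follow-up efficacy descriptive, and section 1.3 does the same for the whole study. The contrast was never randomized, since Arm 2's reference point comes after a year of NA in those still on study. All of that stands, and it limits the consequence to interpretation.

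A reader might infer a definite bias of so many points. The SAP does not support that. It links high HBsAg to ALT elevations, not to the responder rate, so even the direction for the composite endpoint is an assumption. Many offsets in the table are smaller than one Arm 2 participant.

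A reader might also infer that no high-HBsAg placebo participant ever received open-label drug, or that Arm 2 has at most 6 participants. Neither is documented: some may have rolled over before the rule, and 6 is an expectation.

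On Table 1, the second double-blind rule can be made to work, and if the open-label phase is then left missing, follow-up starts correctly. Reading a projected Week 52 date as existing for everyone may not be the intent. So it is too strong to say that no branch can be used. But the first rule, read literally, fails, and the open-label start and end stay unresolved on either route.

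On off-treatment endpoints, sustained response is already tied to having stopped JNJ-3989 (section 5.5.1.1.6). Only the relapse and flare definitions and the compliance denominator are loose.

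HBsAg subgroups exist (section 2.4.1), but they cut baseline at 10,000 or more, or screening jointly with HDV RNA. They do not follow the roll-over rule and are not applied to section 5.5.1.4.

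**Conclusion.** The point holds in limited form. As written, the matched display compares Arm 2 participants selected for lower HBsAg with an unselected Arm 1, on endpoints that include normal ALT, and section 5.5.1.4 does not acknowledge it. The numerical size cannot be established from the SAP; 1 to 20 points is only what the assumed ranges produce. With about 6 participants expected in Arm 2, any open-label percentage is coarse.

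Table 1 does not give a complete set of phase dates for a participant who finishes placebo and moves to follow-up. This can misplace untreated visits and adverse events whatever the size of the selection effect.

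It would be wrong to infer that the main efficacy results are compromised: the primary and key secondary endpoints are at Week 48, before any roll-over, and no type I error claim remains. The roll-over rule itself is not questioned. This should be fixed before the affected outputs are programmed, but the study's main conclusions do not depend on it.

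**What to change.** 1. In section 5.5.1.4, make the main matched display the Part 2 participants in both arms with HBsAg at or below 10,000 IU/mL at screening and at baseline. Applying the limit to both arms also handles anyone who rolled over before the rule. Show all participants as supportive and state the number excluded per arm. The expected offset from this selection is then zero; the year of prior NA in Arm 2 remains and should be noted. The section should also say that not all of Arm 2 switches at Week 52.
2. In Table 1, define the open-label start by an actual open-label JNJ-3989 dose. Add a branch for Part 2 placebo participants who do not roll over: open-label phase missing, double-blind phase ending at the end of the double-blind period with the 5-day extension for adverse events and concomitant medications kept, and follow-up from the next day.
3. State that participants never exposed to JNJ-3989 are excluded from the JNJ-3989 off-treatment relapse and flare endpoints (sections 5.5.1.1.4 and 5.5.1.1.5) and from Arm 2 open-label compliance (section 4.7).

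The cost is SAP wording and derivation code, plus a smaller Arm 1 in one descriptive display. Under the assumed f of 10% to 50%, the main display would have about 24(1 − f) = 21.6 down to 12 in Arm 1, against 6(1 − f) = 5.4 down to 3 in Arm 2.

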5.1. Analysis Specifications

In general, continuous variables will be summarized using descriptive statistics including the number of participants, mean, standard deviation (SD), two-sided 95% confidence interval (CI), median, and range). Binary or categorical variables will be summarized using the number and percentage of participants in each category. For time-to-event variables, a summary table including number of participants included in the analysis, number of participants censored, 25th and 75th percentiles and median time-to event will be shown. Descriptive summaries will be provided by stratification factors presence of compensated cirrhosis at screening (yes or no) (Part 1 only), HDV RNA testing laboratory location (China versus outside China), and HBeAg status at screening (positive vs negative). Graphic displays will also be used to summarize the data.

5.1.1. Virology Data Handling Rules

Those measurements collected from screening visit to the end of study will be handled according to the following rules in [Table 4](#).

Table 4: Data Handling Rules for HDV and HBV Virology and Serology Assessments

HDV parameter	LLOQ	ULOQ	Imputed Values	
			If value < LLOQ	If value > ULOQ
HDV RNA	For outside of China : LLOQ = 63 IU/mL LOD = 14 IU/mL	NA	For outside of China : Main imputation: If <LLOQ 31.5 IU/mL Exploratory Imputation: If LLOQ TD: 31.5 IU/ml If LLOQ TND: 15.75 IU/ml ^(a)	NA
HBV parameter	LLOQ	ULOQ	Imputed Values	
			If value < LLOQ	If value > ULOQ
HBsAg	0.05 IU/mL	124,925.00 IU/mL w/o dilution 249,750.00 IU/mL with dilution	0.025 IU/mL ^(a)	137,417.5 IU/mL ^{(b)(c)} w/o dilution 274,725.00 IU/mL ^(c) with dilution
HBeAg	0.11 IU/mL	1,400.00 IU/mL w/o dilution 7,000.00 IU/mL with dilution	0.055 IU/mL ^(a)	1,540.00 IU/mL ^{(b)(c)} w/o dilution 7,700.00 IU/mL ^(c) with dilution
HBcrAg	3.0 log ₁₀ U/mL	7.0 log ₁₀ U/mL w/o dilution 9.0 log ₁₀ U/mL with dilution	2.7 log ₁₀ U/mL	7.7 log ₁₀ U/mL ^{(b)(c)} w/o dilution 9.9 log ₁₀ U/mL ^(b) with dilution
HBV DNA	20 IU/mL For Roche CAP/CTM Assay 10IU/mL for Roche COBAS 6800 assay	170,000,000 IU/mL w/o dilution	If < LLOQ: 5 IU/mL	187,000,000 ^{(b)(c)} w/o dilution
HBV RNA	LLOQ = 2.939 log ₁₀ cp/mL (i.e 869 cp/mL) LOD = 1.398 log ₁₀ cp/mL (i.e 25 cp/mL)	NA	If < LOD or target not detected then 1.114 log ₁₀ cp/mL (13 cp/mL)	NA
Anti-HBs	5mIU/mL	10000.0 mIU/mL	2.5 mIU/mL ^(a)	11000.0 mIU/mL ^(b)

Key: NA=Not applicable

(a) LLOQ/2

(b) ULOQ+(ULOQ/10)

(c) If the original result > ULOQ, then take the re-test value (i.e. diluted result). If the diluted result is not available, use the imputed value indicated in this table

All other viral activity data with values <LLOQ which are not included in the data handling rules above will be imputed by the absolute value divided by 2.

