5.3. Primary Efficacy Endpoint 5.4. Key Secondary Endpoints	Removed sensitivity estimators and per protocol analyses.	Due to stopped enrollment, the study will only have descriptive analyses.
2.4. Definition of Subgroups 5.3.3. Subgroup Analyses	Removed some of the subgroup analyses.	Due to stopped enrollment and smaller sample size, some of the subgroup analyses are no longer needed.
5.6.1.6. Relationship Between On-Treatment ALT Elevations, Efficacy and Safety Endpoints, and Baseline Characteristics	Added analyses on the relationship between On-Treatment ALT elevations and Efficacy and Safety Endpoints, and Baseline Characteristics	Due to safety concern and ALT Flares, new analyses were included
5.1.1. Virology Data Handling Rules	Changed Imputation Rules for laboratory values and LLOQ Values	The focus of the analyses for HBV DNA are on < LLOQ. New assay with lower LLOQ value is used for HBV DNA from Jne 2023 and therefore LLOQ value was updated.
Throughout the SAP	Other changes, clarifications, and corrections made throughout the document.	To be aligned with other SAPs within the Hepatitis B project

Amendment 4

Overall rationale for the Amendment: This amendment aims to align the Statistical Analysis Plan (SAP) to the Protocol Amendment #3 issued on December 6, 2021 which was submitted in the context of data supporting start of Part 2. Protocol amendment #3 introduces updated inclusion criteria for the population enrolled in Part 2: cirrhotic participants will no longer be enrolled and adapted inclusion criteria for HBsAg and HDV RNA are provided. In addition, guidance to continue NA treatment until the last study visit and the discontinuation criteria of prolonged ALT elevation (as recommended by FDA) is introduced.

Protocol Amendment #3 also includes optional liver biopsies for Part 2 participants to allow a better understanding of the impact of JNJ-3989 treatment on viral and immune markers in the liver in these HBV/HDV co-infected participants, described as new exploratory endpoints. This amendment provides details on the analyses for those endpoints.

Additional changes are implemented for the simulations related to the sample re-estimation IA planned during the double-blind phase of Part 2 as the enrollment rate has been updated for Part 2 from 0.23 to 0.27 patient/site/month.

Main Changes		
Section Number and Name	Description of Change	Rationale

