 - Participants with HBsAg \geq 10,000 IU/mL
 - HBV DNA at baseline (quantitative): values in IU/mL and \log_{10} IU/mL
 - HBV DNA category at baseline (quantitative: IU/mL):
 - Participants with HBV DNA < LLOQ (20 IU/mL or 10 IU/mL for the new assay)
 - Participants with HBV DNA < 60 IU/mL
 - Participants with HBV DNA < 2,000 IU/mL
 - Participants with HBV DNA < 20,000 IU/mL
 - Participants with HBV DNA \geq 20,000 IU/mL
 - HBV RNA (quantitative): values in copies/mL and \log_{10} copies/mL
 - HBV RNA category at baseline (quantitative: copies/mL):
 - Participants with HBV RNA < LOD
 - Participants with HBV RNA < LLOQ
 - Participants with HBV RNA \geq LLOQ
 - Hepatitis B core related antigen (HBcrAg) at baseline (quantitative): values in \log_{10} U/mL
 - HBcrAg category at baseline (quantitative: \log_{10} U/mL):
 - Participants with HBcrAg <3 \log_{10} U/mL
 - Participants with HBcrAg \geq 3 \log_{10} U/mL-<4 \log_{10} U/mL
 - Participants with HBcrAg \geq 4 \log_{10} U/mL
 - HBsAg Antibody (Anti-HBs) category at baseline (quantitative: mIU/mL):
 - Participants with Anti-HBs <10 mIU/mL
-

- Participants with Anti-HBs \geq 10 mIU/mL
- HBeAg Antibody (Anti-HBe) status at baseline (qualitative): Positive, Negative, Borderline
- Anti-HDV status at baseline: Positive, Negative
- Alanine aminotransferase (ALT) at baseline:
 - Baseline ALT values (U/L)
 - Baseline ALT toxicity grade according to DAIDS
 - Baseline ALT categorization ($\leq 1.0 \times \text{ULN}$, $> 1.0 \times \text{ULN}$ to $< 2.5 \times \text{ULN}$, $\geq 2.5 \times \text{ULN}$)
- Stage of liver fibrosis: F0, F1, F3 or F4
- HBV genotype (using the INNO-LiPA or sequence based HBV genotyping data): Genotype A, B, C, D, E, F, G, H, I, J and Unknown

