5.5.1.1.9. Virologic HBV Breakthrough

Virologic HBV breakthrough is defined as having a confirmed on-treatment HBV DNA increase by $>1 \log_{10}$ from on-treatment nadir level in participants who did not have on-treatment HBV DNA <LLOQ or a confirmed on-treatment HBV DNA level >200 IU/mL in participants who had on-treatment HBV DNA <LLOQ.

In addition, participants who experience a virologic breakthrough followed by on-treatment biochemical flare (see Section 5.5.1.1.11) will be evaluated.

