5.5.1.1.11. HBV Flares

The criteria based on blood markers/lab tests for each of the flare types are defined as below.

a) HBV Virologic flare is defined as follows:

Derivation 1. This derivation of virologic flare will be assessed only for those participants who are off-treatment and had HBV DNA <LLOQ at the last observed point on-treatment.

The start date of a confirmed virologic flare is defined as the first date of two consecutive visits with HBV DNA > 200 IU/mL. The end date of the same confirmed virologic flare is defined as the first date when HBV DNA value returns to ≤ 200 IU/mL or the date of treatment restart (ie JNJ-3989 and/or NA), whichever comes first. Each virologic flare will be categorized based on the confirmed (ie two consecutive values) peak HBV DNA above any of the three thresholds within the start and end date of that flare as follows: 20,000 IU/mL 2,000 IU/mL and 200 IU/mL.

- 1 (Yes) = confirmed HBV DNA > peak threshold
- 0 (No) = at least one off-treatment HBV DNA measurement available and not meeting the criteria of confirmed HBV DNA > peak threshold.
- 2 (Not applicable) = no off-treatment HBV DNA quantitative measurements available.

Derivation 2. This derivation of virologic flare will be assessed only for those participants who are off-treatment and had HBV DNA \geq LLOQ at the last observed point on-treatment.

The start date of a confirmed virologic flare is defined as the first date of two consecutive visits with HBV DNA log₁₀ increase > 1 log₁₀ from EOT. The end date of the same confirmed virologic flare is defined as the first date when HBV DNA log₁₀ increase from EOT returns to \leq 1 log₁₀ or the date of treatment restart (ie JNJ-3989 and/or NA), whichever comes first. Each virologic flare will be categorized based on the confirmed (ie, two consecutive values) peak HBV DNA increase above any of the three thresholds within the start and end date of that flare as follows: 1 log₁₀, 2log₁₀, 3 log₁₀.

- (Yes) = confirmed HBV DNA increase from EOT > peak threshold
- 0 (No) = at least one off-treatment HBV DNA measurement available and not meeting the criteria of confirmed HBV DNA increase from EOT > peak threshold.
- 2 (Not applicable) = no off-treatment HBV DNA quantitative measurements available.

b) Off-treatment HBV biochemical flare is defined as follows:

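### HBV DNA is read against two assay limits (20, then 10 IU/mL) with no common cut-off, so a stable 10 to <20 IU/mL changes category and appears to rise when the assay changes

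*SAP*

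**What the plan says.** SAP Section 5.1.1, Table 4, gives the HBV DNA LLOQ by assay as "20 IU/mL For Roche CAP/CTM Assay 10IU/mL for Roche COBAS 6800 assay", and the imputed value for both as "If < LLOQ: 5 IU/mL". Section 4.2.1 confirms that the category is read per assay: "< LLOQ (20 IU/mL or 10 IU/mL for the new assay".

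The timing appears only in the Amendment 5 table of main changes: "New assay with lower LLOQ value is used for HBV DNA from Jne 2023 and therefore LLOQ value was updated". The same entry says "The focus of the analyses for HBV DNA are on < LLOQ".

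Below-LLOQ status is used in three ways:

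- **As an endpoint.** It is an HBV DNA cut-off over time (Section 5.5.1.1.10), beside reductions from baseline of at least 1, 2, 3 and 4 log10.
- **To select the breakthrough rule (Section 5.5.1.1.9).** A confirmed rise of >1 log10 from on-treatment nadir applies "in participants who did not have on-treatment HBV DNA <LLOQ". A confirmed level >200 IU/mL applies to those who did have such a result.
- **To select the virologic flare derivation (Section 5.5.1.1.11).** Derivation 1 (>200 IU/mL) is for off-treatment participants who "had HBV DNA <LLOQ at the last observed point on-treatment". Derivation 2 (>1 log10 above EOT) is for those at or above LLOQ at that point.

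Section 5.5.2.2.3.2 also plans an MMRM of HBV DNA change from baseline over the double-blind phase. No section sets a common limit, a bridging rule or a sensitivity analysis across the assays.

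**The concern.** The stated focus of the HBV DNA analyses is a category whose meaning changes during the study. A result between the two limits is unquantified before the change and quantified after it. An unchanged viral level can then look like a loss of suppression, shorten a decline from baseline, and be judged for breakthrough or flare by a different rule. At stake are the over-time below-LLOQ proportions, the change-from-baseline summaries and reduction cut-offs, part of the double-blind MMRM, and the choice of event rule for some participants.

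**Working it through.** **Inputs.** LLOQ 20 (old) and 10 IU/mL (new), imputed value 5 IU/mL (Table 4); switch in June 2023 (Amendment 5 table); event limits of 200 IU/mL and 1 log10 (Sections 5.5.1.1.9 and 5.5.1.1.11). Assumption: both assays return the same number for the same sample wherever both quantify it.

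**Where the 5 comes from.** Table 4 attaches no formula to the HBV DNA cell. 10/2 = 5 matches half the new LLOQ; 20/2 = 10 does not match. Because the LLOQ/2 footnote is not attached to this cell, 5 breaks no stated rule.

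**Apparent change for an unchanged true value v, old assay then new.**

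| True value (IU/mL) | Old | New | Apparent change |
|---|---|---|---|
| <10 | 5 | 5 | 0.00 |
| 10 | 5 | 10 | log10(10/5) = 0.30 |
| 15 | 5 | 15 | log10(15/5) = 0.48 |
| 19 | 5 | 19 | log10(19/5) = 0.58 |
| just under 20 | 5 | v | just under log10(20/5) = 0.60 |
| ≥20 | v | v | 0.00 |

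**Reduction cut-offs.** With baseline 100 and a true value of 15, the old assay gives log10(100/5) = 1.30 and meets the 1 log10 cut-off. The new assay gives log10(100/15) = 0.82 and does not.

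**Event rules.** The effective >1 log10 limit is 10 × the nadir or EOT value.

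| Nadir or last on-treatment value | Old assay | New assay |
|---|---|---|
| 10 | >200 | >100 |
| 12 | >200 | >120 |
| 15 | >200 | >150 |
| 19 | >200 | >190 |

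With an LLOQ of 20 the two rules meet, since 10 × 20 = 200. With an LLOQ of 10 they do not: a last value just under 10 is judged against >200, and a last value of 10 against >100.

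**Who crosses the switch** (taking 1 June 2023, since only the month is given).

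- All 22 Part 1 participants were enrolled by SAP Amendment 3 (8 July 2021), so their 52 double-blind weeks ended by about July 2022, on the old assay.
- In Part 2, Week 52 (day 365) falls on or after the switch for those first dosed from about 2 June 2022 (364 days earlier), and Week 48 (day 337) for those first dosed from about 30 June 2022. Enrolment was halted in December 2022, so baselines are on the old assay.
- Week 144 (day 1009) falls before the switch only for those first dosed before about 27 August 2020. Part 2 followed Protocol Amendment 3 of 6 December 2021, so every Part 2 completer has EOT on the new assay.

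**Would half of each LLOQ be better?** No. With 10 then 5, a stable value <10 shows a false fall of log10(5/10) = −0.30, and a stable 10 to <20 still shows a rise of 0 to 0.30.

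**The case against.** The strongest defence is that the shared 5 is a reasonable choice. It gives no change for anyone below 10 IU/mL on both assays and avoids the false fall that half of each LLOQ would create. That stands: the fault is the moving limit, not the shared value.

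A reader might infer that the false rise creates breakthroughs or flares. It does not. It stays below 0.60 log10, the rules need a confirmed >1 log10 or >200 IU/mL, and the imputed 5 never enters a >1 log10 rule because those rules apply only to participants with quantified values.

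A reader might also infer that event thresholds change by calendar date for everyone. The written limits do not change; only the choice between them can. For breakthrough, anyone with an earlier on-treatment result below 20 on the old assay stays under >200 IU/mL. For flares, off-treatment in the HBV endpoints means off both JNJ-3989 and NA (Section 5.5), and Part 2 completers all have EOT on one assay. The old/new contrast is therefore mainly limited to participants whose last on-treatment value came before the switch and who also stopped NA.

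Finally, both randomised arms meet the switch over the same calendar period, which limits bias between arms in the MMRM. It does not repair the within-arm proportions and changes over time, which are reported by arm.

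**Conclusion.** The concern holds for true values of 10 to <20 IU/mL. Followed as written, the plan turns a stable value in that band into a false rise of 0.30 to just under 0.60 log10 and removes below-LLOQ status. Over-time proportions, changes from baseline and reduction cut-offs are exposed. The MMRM is exposed only for Part 2 participants whose double-blind phase spans the switch. Rule selection is affected for breakthrough only in participants with no earlier on-treatment below-LLOQ result, and for flares according to the assay that gave the last on-treatment value.

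The weight is moderate. The primary endpoint is HDV RNA with ALT, baseline HBV DNA enters it only as an imputation covariate, baseline subgroups are little affected, and the study is now descriptive. The document does not show how many participants lie in the band. The arms are small, though: 30 participants at 4:1 is about 24 and 6, so one reclassification moves a Part 2 proportion by about 1/24 = 4 or 1/6 = 17 percentage points.

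**What to change.** In the SAP analyses, define one HBV DNA cut-off of <20 IU/mL for both assays at all time points. Use it wherever below-LLOQ status defines a category (Sections 2.4.1, 4.2.1 and 5.5.1.1.10) or selects the breakthrough or flare derivation (Sections 5.5.1.1.9 and 5.5.1.1.11). Set all values <20 IU/mL to one imputed value. A stable value below 20 then shows a change of 0.00, and one event rule applies whatever the date.

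Keeping 5 leaves existing declines to below 20 unchanged. If 10 is preferred, state that every such decline shrinks by log10(10/5) = 0.30. For example, a baseline of 80 falling below the limit goes from log10(80/5) = 1.20 to log10(80/10) = 0.90 and no longer meets the 1 log10 cut-off.

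Show <10 IU/mL as an additional row for new-assay visits only, and give the switch date beside Table 4. The cost is a recode and the loss of the 10 to <20 IU/mL resolution in the main tables. These changes concern SAP derivations only, not participant management.
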